9.5.5 Completion/Discontinuation of Subjects

For purposes of entering subject disposition in the eCRF, a subject will be considered to have completed the study per protocol after the End of Study visit has been completed. The subject may elect to discontinue the study at any time for any reason. Subjects who discontinue study drug prematurely at any time after randomization at Visit 3 (Study Baseline) will be encouraged to return to the site as soon as practicable (preferably within 7 days). These subjects will be encouraged to continue to complete all study assessments (excepting PK samples, which will not be taken), including the Sleep Diary, and to return for all subsequent clinic visits, without the administration of study medication.

Subjects who agree will undergo an EDD Visit, during which all assessments will be conducted that would be made at an ET visit (except the T-BWSQ). These subjects need not attend the next regularly scheduled visit if this falls within the visit window of the next visit. Subjects who discontinue early from study drug are considered on study as long as they return for their regularly scheduled visits.

Subjects who do not agree to this will undergo an ET Visit and an EOS Visit, as described in the Schedule of Procedures/Assessments (Table 3). (revised per Amendment 01)

Subjects who withdraw because of an AE should also undergo a urine drug test.

If the investigator or sponsor discontinues a subject from the study prematurely, the investigator will promptly explain to the subject involved that the study will be discontinued for that subject and will provide appropriate referral for medical treatment and other necessary measures for the subject. A subject who has ceased to return for visits will be followed up by mail, phone, or other means to gather information such as the reason for failure to return, the status of treatment compliance, the presence or absence of AEs, and clinical courses of signs and symptoms. This information will be recorded in the CRF.

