3.2 Study Subjects

3.2.1 Definitions of Analysis Sets

Safety Analysis Set: The Safety Analysis Set is the group of subjects who received at least 1 dose of randomized study drug and had at least 1 postdose safety assessment.

On-Treatment Safety Analysis Set: On-Treatment Safety Analysis Set is the group of subjects who received at least 1 dose of lemborexant and had at least 1 post dose safety assessment.

Full Analysis Set (FAS): The FAS is the group of randomized subjects who received at least 1 dose of randomized study drug and had at least 1 postdose primary efficacy measurement.

On-Treatment Full Analysis Set (FAS): On-Treatment FAS is the group of subjects who received at least 1 dose of lemborexant and had at least 1 post dose primary efficacy measurement.

6-Month Completer Analysis Set: The 6-Month Completer Analysis Set is the group of subjects in the FAS who had all efficacy assessments up to and including Month 6 (ie, Week 1 and Months 1 to 6 visits) without missing primary or key secondary efficacy assessments at any of these visits.

PK Analysis Set: The PK Analysis Set is the group of subjects who have at least 1 quantifiable lemborexant plasma concentration or its metabolites, with adequately documented dosing history.

PK/PD Analysis Set: The PK/PD Analysis Set is the group of subjects receiving either lemborexant or PBO who have efficacy or safety data with documented dosing history. In addition, subjects receiving lemborexant should have at least 1 quantifiable lemborexant concentration data point as per the PK Analysis Set.

Per Protocol Analysis Set (PP): The PP is the group of subjects who sufficiently complied with the protocol. This analysis set will include all subjects in the Full Analysis Set who sufficiently complied with the protocol during Period 1. The criteria for exclusion in this analysis set are listed below:

- Violated inclusion/exclusion criteria
- Duplicate randomization
- Missing primary efficacy assessment
- Prohibited concomitant medication

- Study drug not administered
- Incorrect study drug kit dispensed
- Non compliance of study medication

Subjects who met any of the criteria listed above will be excluded from the PP due to possible introduction of bias.

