3.6.1 Treatment Definitions

For visit-based Safety data (ie, laboratory values, vital signs, ECGs, etc) data will be summarized by treatment (LEM5, LEM10) and duration of exposure to treatment (3, 6, 9 and 12 months). Treatment groups are LEM5 and LEM10, and include both (a) LEM Period 1 subjects on the On-Treatment Safety Analysis Set using the change from Study Baseline and (b) LEM Period 2 subjects previously receiving PBO on the On-Treatment Safety Analysis Set using the change from Period 2 Baseline. Summaries of exposure, AEs, TEMAV, clinically abnormal vital sign and ECG values will be summarized for:

- Period 1 data, where treatment groups are PBO, LEM5 and LEM10 in the Safety Analysis Set (ie, subjects who received at least 1 dose of study drug in Treatment Period 1)

- 12-month LEM exposure, where treatment groups are LEM5 and LEM10 in the On-Treatment Safety Analysis Set (ie., subjects who received at least 1 dose of lemborexant), where data will be summarized by exposure to treatment (3, 6, 9 and 12 months)

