3.6.3 Adverse Events

The AE verbatim descriptions (investigator terms from the eCRF) will be classified into standardized medical terminology using the MedDRA. Adverse events will be coded to the MedDRA (Version 17.0 or higher) lower level term closest to the verbatim term. The linked MedDRA PT and primary system organ class (SOC) are also captured in the database.

Only those AEs that are treatment-emergent will be included in summary tables. All AEs, treatment-emergent or otherwise, will be presented in subject data listings. AEs will be classified as TEAEs up to 14 days after the last study treatment (see below).

A TEAE is defined as an AE that emerges during treatment (including the Run-In period up to 14 days after the last dose of study drug from the first dose of study drug), having been absent before the randomized study medication is started or

- Reemerges during active treatment, having been present at pretreatment (before the randomized study medication is started) but stopped before treatment, or
- Worsens in severity during active treatment (after randomized study medication starts) relative to the pretreatment state, when the AE is continuous.

Separately, a TEAE during each Period (ie, Run-In, Treatment Period 1 or Treatment Period 2) is defined as:

1. TEAE during the Run-In: AE that emerges prior to the date of first dose in Treatment Period 1 or the date of last dose in Run-In + 14 days, whichever comes earlier.
2. TEAE during Period 1: AE that emerges after the date of first dose in Treatment Period 1 but prior to (a) the date of first dose in Period 2 or (b) the date of last dose in Treatment Period 1 + 14 days, whichever comes earlier.
3. TEAE during Period 2: AE that emerges after the date of first dose in Treatment Period 2 but prior to the date of last dose in Treatment Period 2 + 14 days, whichever comes earlier.

Adverse events will be summarized using the Safety Analysis Set and On-Treatment Safety Analysis Set by treatment groups.

The number (percentage) of subjects with TEAEs during the Run-In Period will be summarized by SOC and PT.

The following summary tables will be produced for the Period 1 (Safety Analysis Set) and On-Treatment (On-Treatment Safety Analysis Set) separately.

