3.6.4 Laboratory Values

Laboratory results will be summarized using Système International (SI) units, as appropriate. With the exception of urinalysis, all quantitative parameters listed in [protocol Section 9.5.1.5.3 Laboratory Measurements](#), the actual value and the change from Study Baseline will be summarized at each scheduled visit using descriptive statistics by treatment group. The change from Study Baseline/Treatment Period 2 Baseline (as appropriate) will also be repeated for the 12-month LEM exposure (On-Treatment Safety Analysis Set), summarized by treatment group and duration of exposure.

For urinalysis, the actual and the change from baseline of pH and specific gravity will be summarized at each visit by treatment group. Analysis of changes from baseline will be based on the number of subjects with both nonmissing baseline and relevant postbaseline results.

Laboratory test results will be assigned a low, normal, high (LNH) classification according to whether the value was below (L), within (N), or above (H) the laboratory parameter's reference range. Shifts from Study Baseline (LNH) to each scheduled visit will be provided by treatment group for each laboratory parameter based on Safety Analysis Set. The shift tables will also be repeated for the 12-month LEM exposure (On-Treatment Safety Analysis Set), summarized by treatment group and duration of exposure.

The Sponsor's Grading for Laboratory Values ([Appendix 1](#)) presents the Eisai criteria that will be used to identify subjects with treatment-emergent markedly abnormal laboratory values (TEMAV). Except for phosphate, a TEMAV is determined if a postbaseline grade increases from baseline and the postbaseline grade is greater than or equal to a grade of 2. For phosphate, a TEMAV was defined as a postbaseline value with an increase from baseline to a grade of 3 or higher.

The number (percentage) of subjects with TEMAVs will be summarized by treatment group using the Safety Analysis Set. The number (percentage) of subjects with TEMAVs will be produced separately for the Period 1, up to 12-months treatment, up to 6-months treatment and On-Treatment. When displaying the incidence of TEMAVs, each subject will be counted

once in the laboratory parameter high and in the laboratory parameter low categories, as applicable.

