6.2.3 Visit Windowing

For the laboratory values, ECG, vital signs, weight, eC-SSRS, T-BWSQ, PGI-Insomnia, WPAI-GH and EQ-5D-3L, the following visit windowing rule in [Table 10](#) will be applied based on measurements from unscheduled visits and early termination visits to attain the measurement for analysis for the given scheduled visit.

Table 10 Windowing Rules for Safety Endpoints

Visit	Target Visit Day (in study days)	Visit Window (in study days)
Visit 4 (Month 1)	30	2 - 45
Visit 5 (Month 2)	60	46 - 75
Visit 6 (Month 3)	90	76 - 135
Visit 9 (Month 6)	180	136 – Prior to the date of first dose of Period 2 If subjects discontinue treatment, the visit window will be 136 – 187
Visit 12 (Month 9)	270	The date of first dose in Period 2 - 315 If subjects discontinue treatment, the visit window will be 188 – 315
Visit 15 (Month 12)	364	316 - 371
End of Study (EOS)	378	Nominal visit (ie., the visit captured in eCRF will be used)

In case of multiple assessments within the same visit window, the assessment closest to the target visit day will be used in data analyses; in the event of two assessments being equally close to the scheduled visit day, the latest assessment in time will be used.

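### The 12-month lemborexant exposure summaries have no cut-off after the last dose for visit-based data and no rule placing a visit in an exposure column, so off-drug values can be counted as on-treatment, most clearly as markedly abnormal laboratory values

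*SAP*

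**What the plan says.** - **Follow-up off drug.** Protocol 9.5.5 encourages subjects who stop study drug to complete all assessments except PK samples and "to return for all subsequent clinic visits, without the administration of study medication". They count as on study while they attend.
- **Analysis sets.** SAP 3.2.1: "On-Treatment Safety Analysis Set is the group of subjects who received at least 1 dose of lemborexant" and had one post-dose safety assessment. Likewise "On-Treatment FAS is the group of subjects who received at least 1 dose of lemborexant" and had one post-dose primary efficacy measurement. Both sets select subjects, not records.
- **Tables.** For visit-based safety data, SAP 3.6.1 says "data will be summarized by treatment (LEM5, LEM10) and duration of exposure to treatment (3, 6, 9 and 12 months"). It lists exposure, AEs, TEMAVs, and abnormal vital sign and ECG values for the same 12-month LEM exposure summary. SAP 3.4 sets up matching efficacy summaries on the On-Treatment FAS.
- **Windows.** SAP 6.2.3, Table 10, works in study days. For Month 6: "If subjects discontinue treatment, the visit window will be 136" to 187. For Month 9: "If subjects discontinue treatment, the visit window will be 188" to 315. Month 12 is 316 to 371, with no on-drug condition.
- **Time limits.** SAP 3.6.3: "AEs will be classified as TEAEs up to 14 days after the last study treatment". SAP 3.6.4 has no counterpart: "a TEMAV is determined if a postbaseline grade increases from baseline" and reaches the stated grade, with no end date.
- **Definition of exposure.** SAP 3.6.2 defines duration of exposure as last dose date minus first dose date plus one. It sits under extent of exposure, and nothing says that it governs the visit-based tables.

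**The concern.** Long-term safety over 12 months is a stated purpose of the trial (Protocol 7.2 and 9.1.2). The exposure tables are where a reader will look for laboratory, vital sign and ECG changes after 6, 9 or 12 months on drug. If off-drug values sit in those columns, two things go wrong.

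First, mean changes from baseline are pulled toward no drug effect wherever the effect fades after stopping. Second, a laboratory abnormality first seen months after the last dose can be credited to the dose. The TEMAV rule shows this most plainly. An event arising 200 days after stopping is not a treatment-emergent AE, yet a laboratory value from the same day can count as a TEMAV in the parallel table.

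**Working it through.** **1. The plan's own retention figures.** SAP section 2 takes 300 per arm, with discontinuation as high as 50% at Month 6 and 60% by Month 12.

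- 300 × (1 − 0.50) = 150 remaining at Month 6.
- 300 × (1 − 0.60) = 120 remaining at Month 12.
- 150 + 150 (the two lemborexant arms at Month 6) + 120 (former placebo subjects at Month 12) = 420 completing 6 months on lemborexant, as stated.

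**2. How long off drug a windowed value can be.** Days off drug = study day of assessment − day of last dose, for a subject randomized to lemborexant on Day 1.

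| Last dose | Month 6 (136–187) | Month 9 (188–315) | Month 12 (316–371) |
|---|---|---|---|
| Day 1 | 135–186 | 187–314 | 315–370 |
| Day 30 | 106–157 | 158–285 | 286–341 |
| Day 90 | 46–97 | 98–225 | 226–281 |

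Under the AE limit the maximum would be 14 days. Table 10 assigns scheduled visits, not exposure columns, so these figures show which values are available to the tables, not where they are placed.

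**3. Possible share of a column that is off drug.** Share = f × S / (A + f × S), where A = subjects on drug, S = subjects who stopped, and f = fraction of stoppers who keep attending. The documents do not give f; the values below are assumptions.

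*6-month column, per dose, at the ceiling.* SAP 3.4 and 3.6.1 pool former placebo subjects into this column. The 150 placebo subjects remaining at Month 6 split into 75 per dose. The 120 remaining at Month 12 make 60 per dose, so 15 per dose have stopped.

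- A = 150 + 60 = 210; S = 150 + 15 = 165.
- f = 20%: 33 / 243 = 13.6%.
- f = 50%: 82.5 / 292.5 = 28.2%.

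*12-month column, per dose, at the ceiling.* Only subjects randomized to lemborexant in Period 1 can reach it.

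- A = 120; S = 180.
- f = 20%: 36 / 156 = 23.1%.
- f = 50%: 90 / 210 = 42.9%.

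*Month 6 records, arms randomized to lemborexant, at an assumed 20% discontinuation.*

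- A = 240; S = 60.
- f = 10%: 6 / 246 = 2.4%.
- f = 50%: 30 / 270 = 11.1%.

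**4. Effect on a mean.** If the drug effect reverses fully after stopping (an assumption), the column mean is (1 − share) × the on-drug mean. Partial reversal gives less dilution.

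**The case against.** The strongest reply is that the plan already defines exposure by dosing. SAP 3.6.2 uses first and last dose dates. SAP 3.4 describes the On-Treatment FAS summaries as being by time on treatment, and the endpoint lists in SAP 3.1 refer to subjects with a given number of months of exposure. On that wording, a subject dosed for 20 days does not belong in a 9-month column. A reader might infer from Table 10 that such a subject will appear there. The documents do not support that. Table 10 assigns scheduled visits, and it cannot serve as the exposure map, because a former placebo subject at study day 270 has had about 270 − 180 = 90 days of lemborexant. Its discontinuation clauses are also needed for the by-visit summaries, since the ordinary Month 6 and Month 9 windows depend on a first Period 2 dose that Period 1 stoppers lack.

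Some limits do exist. SAP 3.6.6 counts QTcF thresholds during treatment, though it does not define that. Table 9 can cap the Month 12 diary window at last dose + 1, but only for those completing 12 months of treatment. The 14-day AE limit defines treatment emergence, not exposure, so it should not be read as a competing exposure rule. Protocol 9.4.7.2 requires subjects who start a prohibited or new insomnia treatment to leave the study even after stopping drug, with a limited exception, which would lower attendance. Derivations and table shells are in separate documents that may hold the missing rule.

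All of this stands, and it makes the outcome permitted rather than certain. It does not close the gap. No sentence applies the 3.6.2 definition to the visit-based tables, and the TEMAV rule has no end date on any reading. SAP 3.6.4 also still names up-to-12-month and up-to-6-month treatment summaries that 3.6.1 does not define.

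**Conclusion.** The point holds as a gap in the rules. Nothing in the SAP stops off-drug labs, vital signs, most ECG values, TEMAVs or by-exposure diary values from being counted in the on-treatment exposure summaries, and nothing says how a visit reaches an exposure column. The case is clearest for TEMAVs.

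The size cannot be fixed from the documents. The 14% to 28% (6-month column) and 23% to 43% (12-month column) figures combine the plan's ceiling on discontinuation, which is not its expectation, with an assumed 20% to 50% attendance. At an assumed 20% discontinuation and 10% to 50% attendance, the figure is about 2% to 11% of Month 6 records in the arms randomized to lemborexant. All these shares suppose that stoppers' values are placed by visit rather than by dosing duration.

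A reader might go further and infer that the trial's efficacy conclusions or its counts of long exposure are compromised. They are not. The affected tables are descriptive, with no hypothesis tests for safety or for efficacy beyond Month 6. The primary and key secondary analyses use off-drug data by design, and the exposure counts in SAP 3.6.2 rest on dose dates.

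**What to change.** In SAP 3.4, 3.6.1, 3.6.4 and 6.2.3:

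- State that exposure columns are assigned by days since first lemborexant dose while on drug, consistent with SAP 3.6.2, and that Table 10 serves the by-visit summaries only.
- Restrict the 12-month LEM exposure summaries of labs, vital signs and ECG, and the on-treatment TEMAVs, to assessments from first lemborexant dose to last lemborexant dose + 14 days, the limit already used for AEs.
- For by-exposure diary endpoints, use mornings up to last lemborexant dose + 1.
- Keep off-drug values in listings and in the Period 1 primary analysis.
- Remove or define the up-to-12-month and up-to-6-month TEMAV summaries in 3.6.4.

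The cost is SAP wording and a date filter on data already collected. The downside is somewhat smaller counts in the later columns. If the programming documents already apply these rules, only the wording is needed.

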Evaluations of safety will be performed on the relevant Safety Analysis Set and On-Treatment Safety Analysis Set, as appropriate. The incidence of AEs, out-of-normal range laboratory safety test variables, abnormal ECG findings, out-of-range vital signs and weight, suicidality (eC-SSRS), and T-BWSQ (including frequency and percentage of subjects with T-BWSQ ≥ 3), along with change from Study Baseline in laboratory safety test variables, ECGs, and vital sign and weight measurements, will be summarized by treatment group and visit using descriptive statistics. This will be repeated for the 12-month LEM exposure (On-Treatment Safety Analysis Set), summarized by treatment group and duration of exposure. (revised per Amendment 06)

Customized MedDRA Queries (CMQ) for AEs that could potentially be considered cataplexy or seizure, somnolence, and related events, and preferred terms related to drug abuse liability, will be summarized. The results of the deliberation of the Adjudication Committee will be reported separately. (revised per Amendment 03)

Other Analyses

Secondary and exploratory endpoints may be additionally presented graphically or analyzed by modeling methods if warranted.

Interim Analysis (revised per Amendments 04 and 05)

No interim analysis is planned for this study.

Sample Size Rationale

The sample size was estimated for the comparison of LEM10 and LEM5 with PBO, with respect to the mean change from Study Baseline at the end of Month 6 of the mean sSOL, mean sSE, and mean

sWASO. This estimate was based on sequential gate-keeping procedure at the 0.05 α -level as described above. There is sufficient power for both the primary endpoint (sSOL) and key secondary endpoints (sSE and sWASO).

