9.7.1.8.6 OTHER SAFETY ANALYSES

The results of eC-SSRS assessments will be listed for each subject. The incidence of suicidal ideation or suicidal behavior will be summarized by treatment group as appropriate. Urine drug test results and pregnancy test results will also be listed.

Withdrawal symptoms will be assessed using the T-BWSQ. The mean score will be summarized by treatment group, and number (percentage) of subjects with a score ≥ 3 will be summarized.

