3.6.7 Other Safety Analyses

3.6.7.1 Columbia-Suicide Severity Rating Scale (C-SSRS)

Suicidality is assessed using a self-rated electronic version of the C-SSRS (eC-SSRS). The eC-SSRS assesses an individual's degree of suicidality, including both suicidal ideation and suicidal behavior. The occurrence of suicidal ideation or suicidal behavior at each visit will be summarized by treatment group using frequency count. A subject will be counted once for each of these categories if at least one question is answered positive belonging to the category.

In addition, self-injurious non-suicidal behavior will also be summarized separately for occurrence in a similar fashion to suicidal ideation and behavior.

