9 MOCK TABLES, LISTINGS, AND GRAPHS

The study TLG shells will be provided in a separate document, which will show the content and format of all tables, listings, and graphs in detail.

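### The SAP's windowing rule can leave a positive eC-SSRS at an early termination visit out of every suicidality table it specifies, and it specifies no any-postbaseline count per subject

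*SAP*

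**What the plan says.** SAP 6.2.3 lists the eC-SSRS among the assessments to which Table 10 applies. The windows "will be applied based on measurements from unscheduled visits and early termination visits to attain the measurement for analysis for the given scheduled visit". Within a window, "In case of multiple assessments within the same visit window, the assessment closest to the target visit day will be used in data analyses"; only on a tie does the later one win. The end-of-study (EOS) visit has its own nominal row. ET has none.

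SAP 3.6.7.1 gives the summary: "The occurrence of suicidal ideation or suicidal behavior at each visit will be summarized by treatment group using frequency count". Self-injurious non-suicidal behavior is handled the same way. The section's rule for counting a subject once merges questions within a category. It does not merge visits.

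SAP 3.6.1 names the outputs produced for Period 1 and for 12-month lemborexant exposure: "Summaries of exposure, AEs, TEMAV, clinically abnormal vital sign and ECG values will be summarized for" those two settings. The eC-SSRS is not among them.

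In the protocol, the Synopsis (Safety Analyses) says that suicidality, with other safety variables, "will be summarized by treatment group and visit using descriptive statistics". Section 9.7.1.8.6 says "The results of eC-SSRS assessments will be listed for each subject" and "The incidence of suicidal ideation or suicidal behavior will be summarized by treatment group as appropriate". Section 9.1.2 and Table 3 place the eC-SSRS at ET and Early Drug Discontinuation (EDD) visits as well as at Months 1, 3, 6, 9 and 12.

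**The concern.** Keeping the value nearest the target day is sensible for a laboratory or vital-sign mean, where one representative value per visit is wanted. For an infrequent safety signal the reader wants to know whether the subject was ever positive. SAP 3.6.6 does this for ECG, by tabulating the maximum postbaseline value for Period 1 and for 12-month exposure. The eC-SSRS has no counterpart.

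Two things follow. First, the ET visit is made when a subject stops drug and leaves the study, and its result can be displaced by an earlier negative in the same window. The suicidality tables may then understate the number of subjects with a positive answer. Second, by-visit counts cannot be turned into a per-subject incidence by arm: one subject positive at two visits looks the same as two subjects positive once each.

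**Working it through.** The documents give no figure on this point to reproduce. The check applies the stated rule to each possible stop day.

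**Inputs**
- Table 10 windows (target day in brackets): Month 1, Days 2-45 (30); Month 2, 46-75 (60); Month 3, 76-135 (90); Month 6, from 136 to before the first Period 2 dose, or 136-187 if treatment is discontinued (180); Month 9, from the first Period 2 dose, or from 188 if discontinued, to 315 (270); Month 12, 316-371 (364).
- Scheduled on-treatment eC-SSRS at Months 1, 3, 6, 9 and 12 (protocol Synopsis and Table 3). None is scheduled at Month 2.
- Visit tolerance of 4 days at Months 1 and 3 and 7 days from Month 4 on (protocol Table 3, footnote d). The ET visit is preferably within 7 days of stopping (protocol 9.5.5).

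**Assumptions.** Stop days are spread evenly over Days 2-179 and 181-363, so 178 + 183 = 361 days. Period 2 starts on Day 181. Scheduled visits are attended up to and including the stop day and none after it. An ET result in the Month 2 window counts as used.

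**Rule.** With a scheduled eC-SSRS on day v and an ET eC-SSRS on day d in the same window with target t, the ET result is unused when |v − t| < |d − t|.

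**The example.** v = 90, d = 120, t = 90. |90 − 90| = 0 is less than |120 − 90| = 30, so Day 90 is used and the ET positive is not.

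**Stop days on which the ET result is unused**

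| ET visit | Scheduled visits | Stop days affected | Count | Share of 361 |
|---|---|---|---|---|
| On stop day | On target | 31-45, 91-135, 271-315 | 15 + 45 + 45 = 105 | 29.1% |
| On stop day | 4 or 7 days early or late | 35-45, 95-135, 278-315 | 11 + 41 + 38 = 90 | 24.9% |
| 7 days later | On target | 30-38, 90-128, 270-308 | 9 + 39 + 39 = 87 | 24.1% |
| 7 days later | Early | 28-38, 88-128, 271-308 | 11 + 41 + 38 = 90 | 24.9% |
| 7 days later | Late | 34-38, 94-128, 277-308 | 5 + 35 + 32 = 72 | 19.9% |

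Over lags of 0 to 7 days the extremes are 72 and 105.

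**Sensitivity to reading Table 10.** If the discontinuation windows (136-187 and 188-315) are also applied to subjects who stop in Period 2, an ET visit on Days 181-187 falls in the Month 6 window behind the Day 180 visit. That adds 7 days: 105 + 7 = 112, and 112/361 = 31.0%.

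**Sensitivity to stop timing** (first row's settings). Stops only on Days 2-90: 15/89 = 17%. Stops only on Days 91-179: 45/89 = 51%. Stops only on Days 2-30, 46-90, 136-179 or 316-363: 0%.

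**EDD visits, only if windowed like ET.** The SAP does not say that they are. With later visits attended on target, an EDD result is unused on every day in a window with a scheduled eC-SSRS except the target day itself: 146 of 178 in Period 1 and 182 of 183 in Period 2, so 328/361 = 91%. The lowest setting (visits early, 7-day lag, next visit skipped when close) gives 101 + 140 = 241, or 67%.

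**The case against.** By-visit tables match the protocol Synopsis, so the SAP does not depart from the protocol here. That stands. Protocol 9.7.1.8.6 also promises an incidence by treatment group where appropriate, without tying it to visits, and the SAP never withdraws it. The shells are in a separate document, "which will show the content and format of all tables, listings, and graphs in detail", and programming derivations are separate too (SAP 7). An overall count may therefore be planned without being written in the SAP. That cannot be ruled out. What can be said is that the SAP text specifies none, and that its stated selection rule applies to data analyses in general.

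SAP 3.6.1 also summarizes visit-based safety data by duration of exposure. That is still not an any-postbaseline count.

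Patient safety is largely protected by other means. Qualified staff must act on positive responses, the investigator reviews every subject's results for AEs, the DSMB reviews safety data, all results are listed, and ET subjects also have an EOS visit that is not windowed out. These limit the harm. But AE tables recover only positives judged to be AEs, the EOS result is a separate later assessment, and a listing is not a by-arm count.

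The 20% to 29% range varies visit timing while holding stop days uniform, and other stop patterns give 0% to 51% or more. That is fair, so the range is an illustration only. The EDD figures rest on a reading that the SAP does not state, and the point does not need them. The case for unscheduled visits is weaker too, because the eC-SSRS there is at the investigator's discretion.

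**Conclusion.** The concern holds as a statement about the SAP text. Taken together, the windowing rule in 6.2.3 and the by-visit count in 3.6.7.1 allow an ET positive to enter no specified suicidality table, and no specified table gives subjects ever positive by arm. With evenly spread stop days the ET result is unused on 20% to 29% of days, or up to 31% on the literal reading of Table 10. The true share of subjects depends on when they stop, which the documents do not give. No positivity rate or arm difference is given either, so neither the undercount nor its direction between arms can be sized. It is a gap in a safety summary that is worth closing. It does not affect the efficacy conclusions.

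**What to change.** In SAP 3.6.7.1, add the number and percentage of subjects, by treatment group, with any positive postbaseline eC-SSRS, separately for ideation, behavior and self-injurious non-suicidal behavior. Give it for Period 1 (Safety Analysis Set) and for 12-month lemborexant exposure (On-Treatment Safety Analysis Set), using all assessments in the period including ET, EDD and unscheduled ones. In SAP 6.2.3, state that for the eC-SSRS the closest-to-target rule applies to by-visit summaries only.

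The cost is SAP wording and one more table; the data are already collected. SAP 1 provides for such updates if documented and approved before unblinding. The downside is small: the rates may look slightly less favourable, because subjects with more visits have more chances of a positive.
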